2.1 STUDY DESIGN

This Post Authorization Safety Study (PASS) is an observational, non-interventional epidemiologic cohort study using extracted data from proprietary longitudinal patient databases (LPD) in Italy and Spain. This study is being conducted to further characterize selected adverse events of interest among a patient population prescribed BZA, raloxifene, or a bisphosphonate in usual clinical care outside of a randomized clinical trial setting. This PASS is a post-authorization commitment to the Committee for Medicinal Products for Human Use/ European Medicines Agency (CHMP/EMA).

The LPD databases of Italy and Spain contain all drug prescriptions, diagnoses, demographic data, medical history (event data, risk factors) and other types of data electronically collected by participating general practitioners. The eligible population will be constructed from these anonymised LPD databases.

The total study period is planned for 8 years. This study was launched after BZA became commercially available in the participating countries, Italy and Spain. The subject inclusion/accrual period (also referred to as enrolment period) in the database began at the time of commercial launch of BZA in each country (September 2010 in Spain and April 2011 in Italy) and continued for approximately three years from the start of the study, Table 1. The index date for each patient was the date of the first recorded prescription for BZA or raloxifene or bisphosphonates during the enrolment period. Each woman must have at least 6 months of data prior to index prescription date to be included in the analysis, the baseline period. The study therefore consisted of three distinct periods:

- Pre-enrolment period: 6 months before launch day in a country
- Enrolment period: Approximately 3 years from launch day in a country.
- Follow-up period: 5 years of follow-up per patient from the index date.

Table 1: Study timelines by country

	Pre-enrolment Period 6 Months	Enrolment Period 3 Years*	Follow-Up Period 5 Years
Spain	April 1 st 2010- September 30 th 2010	October 1 st 2010- April 30 th 2014	May 1 st 2014- April 30 th 2019
Italy	November 1 st 2010- April 30 th 2011	May 1 st 2011- April 30 th 2014	May 1 st 2014- April 30 th 2019

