* Due to low enrolment/accrual into the study, the original end of the study accrual period was extended from September 30th 2012 in Spain, and April 30th 2013 in Italy, to April 30th 2014 for both Spain and Italy. Extending the accrual period to April 2014 extended the study timelines by 1 year. The new accrual period for Spain is 43 months (October 1st 2010-April 30th 2014) and the new accrual period for Italy is 36 months (May 1st 2011-April 30th 2014).

Patients will be counted in according to the inclusion criteria.

Follow up for each endpoint will be from the index date to whichever of the following occurs first.

1. Endpoint under investigation
2. Last patient visit or completion of 5 years follow up, whichever occurs first.

Each patient will be followed for identification of selected endpoints for a period of up to five years from their index prescription date for BZA, bisphosphonate or raloxifene. The follow up will continue even if the woman discontinues the index medication or switches to a different medication during this five year follow up period. The follow up duration of an individual patient may be shorter than five years if the woman transfers out of the GP office that wrote the index prescription or if she dies.¹ In these situations the data will be censored on the date of last visit. This study will use the Cegedim Longitudinal Patient Database (LPD), an electronic medical records database. However, the Spanish and Italian databases of Cegedim Strategic Data (CSD) do not have recorded events of death and date of death. The discontinued patient's record indicate loss to follow-up for various reasons, such as patients' moving from the areas, patient's change of GPs or other various reasons. The number of patients who are lost to follow-up will be provided. A minimum of a six month history in the LPD database prior to the index date (at least one GP visit, whatever the motive of the visit to GP) is required for inclusion of population, in order to ensure a certain quality of information.

Study Population

The study population will be selected based on the following inclusion criteria and all eligible patients enrolled in this study will be included. No exclusion criteria were applied.

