Any patient with a prescription for BZA (exposed cohort), raloxifene (comparator cohort) and bisphosphonate (comparator cohort) treatment accompanied with diagnosis of osteoporosis will be eligible when they meet other inclusion criteria. The detailed inclusion criteria will be as follows:

1. *Female*
2. *At least one prescription for BZA, raloxifene, or any bisphosphonate during the study inclusion period*
3. *A recorded diagnosis code of osteoporosis on or within 60 days prior to the index prescription date.*
4. *Age of patients ≥ 45 at the index prescription date*
5. *At least 6 months of follow-up data in the electronic medical record system prior to the date of index prescription.*

¹ The event of death and date of death are not recorded in CSD Italian and Spanish database. The discontinued patient's records indicate loss to follow-up for various reasons.

The applicability of the third criterion will be evaluated through performing a sensitivity analysis comparing those with osteoporosis diagnosis within 60 days and those without diagnosis within 60 days. This has become necessary due to a significant number of patients (> 45%) missing a recorded diagnosis of osteoporosis. If the venous thromboembolism rates of the two groups are comparable (i.e., difference within 20%), this criterion will not be included.

Data Source

This study will use the Cegedim Longitudinal Patient Database (LPD), an electronic medical records database that collects clinical data from primary care physician practices in the following European countries i.e., Spain, Italy, Germany, France, Belgium and UK. (In the UK the database is known as The Health Improvement Network (THIN).) For this study the Cegedim LPD in Italy and Spain will be used.

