The Cegedim LPD obtains medical information from proprietary practice management software used during physician office visits to capture clinical data in an electronic medical record system. Physicians use the practice management software developed by Cegedim to maintain electronic medical records of their patients. In each country a panel of physicians using this electronic system volunteered to make available anonymized patient-level information from their practices for clinical research purposes. Since these data are being collected in usual clinical care in a non-interventional way, they reflect routine clinical practice in these countries. The panel of contributing physicians is maintained as a representative sample of the primary care physician population in each country according to age, sex, and geographical distribution. Additionally in most countries (including Spain and Italy), the patient population is representative of the respective country population according to age and sex distribution, as provided by national statistic authorities.

Table 2: Doctor and patient populations in the Cegedim LPD by country

	Italy	Spain
Number of physicians in the panel	700	300
Average number of patients who consulted GP at least once in a year	800,000	320,000

The patient data in the LPD form a nationally representative sample. Data have been collected in Italy since 2004 and in Spain since 2006, providing several years of medical history, including comorbidity and concomitant medication use information. Of the patients included in the Spanish and Italian LPD, there are currently approximately 68,000 women with drug-treated osteoporosis. Between 1 and 6% of these patients are taking raloxifene, depending on the region; most of the rest are prescribed a bisphosphonate (Cegedim, data on file).

Data are entered regularly during usual patient care, submitted daily to the Cegedim coordinating center, cleaned and de-identified, and then made available for research.

Anonymized patient data collected from each GP practice includes:

- *Demographic information (age, gender)*
- *Medical history (event dates, diagnoses, risk factors, referrals to specialists)*
- *Therapeutic history (date/length of prescription, molecule/product, dosage)*
- *Additional information (test results, immunizations, height, weight, blood pressure)*

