5.4 SUBGROUPS

Age stratified randomly selected subgroup

In the current dataset, there are 1,823 patients in the bazedoxifene group and 82,041 patients in the bisphosphonate group. This means that there is more than 40 times the number of subjects in the bisphosphonate group compared to the number of subjects in the bazedoxifene group. To limit the number of patients in the bisphosphonate group, an age stratified random subgroup will be selected. Based on the sample size and relative risk estimates provided in the final study protocol (study protocol section 7.1, Sample size calculation), the 1,823 bazedoxifene subjects will be adequately matched by a ratio of 1:6 bisphosphonate subjects. Therefore $1,823 \times 6 = 10,938$ bisphosphonate treated subjects are needed to be randomly selected from the total of 82,041 bisphosphonate treated subjects.

Selection scheme: The age of subjects in the study will be categorized into 4 groups (45-49, 50-59, 60-69, and ≥ 70). In the bisphosphonate group, the percentage of subjects in each of these age groups is 1.4%, 13.7%, 28.7%, and 56.2% respectively. To maintain the same proportion of subjects in each age group for the bisphosphonate subgroup, there will be $1.4\% \times 10,938 = 153$ bisphosphonate treated subjects randomly selected from the 45-49 age group; $13.7\% \times 10,938 = 1,499$ subjects randomly selected from the 50-59 age group; $28.7\% \times 10,938 = 3,139$ subjects randomly selected from the 60-69 age group; $56.2\% \times 10,938 = 6,147$ subjects randomly selected from ≥ 70 age group.

Incident cases of study endpoints

Women with a history of study end points recorded prior to the index prescription will not be included in the analysis for that specific outcome, but will be analyzed separately as subgroups for each study end point. The analyses of the primary and secondary endpoints will be performed using these incident cases of study endpoints subgroups.

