8.1.4 TIME TO EVENT ANALYSIS

A time to event analysis to compare the risk between treatment cohorts, i.e., the BZA, raloxifene and bisphosphonate treated groups, will be conducted for the primary end point (VTE) and other secondary endpoints if sufficient data are available,

[figure not shown]
The time to an event will be calculated as the time from index prescription date to the incidence date of primary end points. If a patient does not have a primary end point, the treatment duration will be based upon the index prescription date to the last visit or end of follow-up period, whichever comes first.

In order to ensure the exact duration from the start of treatment to the incidence of primary endpoints, a subgroup of newly prescribed patients who were diagnosed with osteoporosis during the enrolment period will be used first.

In the very unlikely event that the number of bisphosphonate or raloxifene patients are less than the number of BZA patients, the analysis will be extended to include bisphosphonate and raloxifene patients whose treatment began prior to the enrolment period. Considering the fact that bisphosphonates and raloxifene were launched before BZA (See the figure below), some patients could have already gotten treatment of bisphosphonates and raloxifene prior to the enrolment period (i.e., before BZA was launched). For such patients the start date will be the first date of treatment for bisphosphonates or raloxifene, available within the database.

Figure 1. Calculation of duration (from start date to the incidence of primary endpoint) for the treatment cohorts

The time to event analysis model will also be used to test for differences in time to event while adjusting for covariates of interest.

This model will take into account the duration to the incidence of the endpoint and control for imbalances in outcome risk factors, as determined based on the baseline descriptive analysis.

The following factors possibly related to the incidence of the primary end point will be considered.

- Treatment group (BZA, raloxifene, and bisphosphonate)
- Age
- BMI
- Reported history of smoking (If the reported frequency of smoking status is low this will be excluded)
- Reported Medical History of Diabetes, Hypertension, Malignancies
- Time since diagnosis of osteoporosis
- Previous treatment for osteoporosis (before index date) or Number of different treatments for osteoporosis in the entire patient history available
- History of DVT or PE

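### No analysis accounts for calendar date of index or, in the pooled data, for country, so bazedoxifene and comparator women may differ in calendar period and in length of recorded history

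*SAP*

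**What the plan says.** SAP 2.1 starts observation by one rule in all three cohorts: "The index date for each patient was the date of the first recorded prescription for BZA or raloxifene or bisphosphonates during the enrolment period". Accrual opened on 1 October 2010 in Spain and 1 May 2011 in Italy. After an extension for low enrolment it closed on 30 April 2014 in both.

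History is open-ended. SAP 2.1 requires at least six months of records before index and sets no upper limit or common window. On the depth of the databases it says: "Data have been collected in Italy since 2004 and in Spain since 2006". SAP 5.4 then removes prevalent outcomes: "Women with a history of study end points recorded prior to the index prescription will not be included in the analysis for that specific outcome".

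SAP 8.2.5 gives two populations for every objective:
- Population a is all bazedoxifene women, all raloxifene women and the 1:6 bisphosphonate sample of SAP 5.4, which is drawn by age group only.
- Population b is incident users, defined in 5.4 as women untreated for osteoporosis for at least six months before index.

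The covariates in SAP 8.1.4 and 8.2.4, and the stratifiers named in SAP 8.1.2 and protocol 7.2, include no index date, index year or calendar period. Country is not listed either, although SAP 8.1 pools the two countries at patient level. The baseline tables in SAP 8.1.1 and 8.2.1 report neither index date nor length of prior record.

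One entry criterion bears on this: "A recorded diagnosis code of osteoporosis on or within 60 days prior to the index prescription date". It is conditional. If VTE rates in women with and without such a code are within 20% of each other, SAP 2.1 says that "this criterion will not be included".

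**The concern.** Bazedoxifene was not on the market before the window opened, so only comparator women can be continuing users of their index drug. SAP 8.1.4 recognises that they may exist: "some patients could have already gotten treatment of bisphosphonates and raloxifene prior to the enrolment period". Under the index rule such a woman enters at her first prescription after the window opens. Bazedoxifene women enter as uptake proceeds.

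Two things then differ between the arms. The five-year outcome window sits at a different calendar period. The stretch of record used to exclude past VTE, and to code comorbidity and prior treatment, also has a different length. A shorter record misses more old events, and a missed old VTE that is coded again, or that recurs, can count as incident. In the pooled data country adds a second source of imbalance, because the two databases start two years apart and SAP 8.1 puts bazedoxifene enrolment at about 1,700 women in Spain and about 40 in Italy.

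The study is a regulatory commitment on an identified risk. As planned, the report would not show a reader whether these imbalances exist.

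**Working it through.** **1. The plan's own figures.** Counting calendar months inclusively, 1 October 2010 to 30 April 2014 is 43 months and 1 May 2011 to 30 April 2014 is 36 months, as SAP 2.1 states. The sample size also reproduces: 1,823 × 6 = 10,938.

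**2. Possible look-back.** Inputs are the database start years and window dates in SAP 2.1. I assume records from 1 January of the start year.

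| | First possible index | Last possible index | Spread |
|---|---|---|---|
| Spain (from 2006) | 4.7 years | 8.3 years | 3.6 years |
| Italy (from 2004) | 7.3 years | 10.3 years | 3.0 years |

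These are maxima. A woman who joined a practice later has less.

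**3. Gap in mean index date, Spain.** The documents give neither the share *f* of comparators who were continuing users nor the shape of bazedoxifene uptake, so both are assumed. Let continuing users be indexed evenly over the first 3 months and all other comparators evenly over 43 months.

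- Comparator mean = *f* × 1.5 + (1 − *f*) × 21.5 months after opening.
- Bazedoxifene mean = 43/2 = 21.5 months (uniform uptake) or 2 × 43/3 = 28.7 months (linearly rising uptake).

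| *f* | Comparator mean | Gap, uniform | Gap, rising |
|---|---|---|---|
| 0 | 21.5 | 0 | 7.2 |
| 0.25 | 16.5 | 5.0 | 12.2 |
| 0.50 | 11.5 | 10.0 | 17.2 |
| 0.75 | 6.5 | 15.0 | 22.2 |
| 0.90 | 3.5 | 18.0 | 25.2 |

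Spreading continuing users over 1 to 6 months instead of 3 moves the *f* = 0.90 uniform gap only between 18.9 and 16.6 months. The *f* = 0 row shows that removing every continuing user still leaves about 7 months if uptake rises.

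**4. Pooled look-back.** The Italian share of comparators is not given. I take *f* from 0.5 to 0.8, both uptake shapes, and the 40 and 1,700 enrolment figures of SAP 8.1 for bazedoxifene. If the Italian comparator share follows the patient numbers in SAP 2.1 (800,000/1,120,000, about 71%), mean maximum look-back is 7.0 to 7.4 years in comparators and 6.6 to 7.2 years in bazedoxifene women. The gap, bazedoxifene minus comparator, is about −0.9 to +0.2 years. At a 30% Italian share it is about +0.2 to +1.2 years. The sign depends on an unknown share.

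**5. Follow-up length.** The last index date plus five years is 30 April 2019, the end of follow-up in SAP Table 1. Late index does not truncate maximum follow-up.

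**6. Events available to stratify.** At the protocol 7.1 reference rate, IRR 1 and five full years, 1,823 × 5 × 1.74/1,000 ≈ 16 bazedoxifene VTEs. Index dates span five calendar years, about 3 events each, or eight half-years, about 2 each.

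**The case against.** The plan already limits continuing users. The 60-day diagnosis criterion would keep out many long-standing patients. Population b restricts to new users for every objective. SAP 8.1.4 says newly prescribed patients are used first, and its remark about pre-enrolment treatment introduces a fallback that it calls very unlikely, in which the start date would be the first treatment in the database. Time since diagnosis and previous osteoporosis treatment are candidate covariates, and protocol 6.3 has a clinical expert review potential VTE cases, which bears on re-coded old events. No document reports a change in GP coding, and five-year windows shifted by a year or two largely overlap.

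The effect on the ratio may also be modest. For a look-back gap of 0.83 to 1.93 years in Spain (*f* 0.5 uniform to 0.8 rising), 10,938 × 1.74/1,000 × gap gives about 16 to 37 comparators with a missed past VTE. If 10 to 25% of them were later counted as incident (an assumption), that is 2 to 9 events against about 95 expected (10,938 × 5 × 1.74/1,000), or 2 to 10%.

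Much of this stands as mitigation, but it does not close the gap:
- The diagnosis criterion may be dropped, and SAP 2.1 reports that more than 45% of patients lack a recorded diagnosis.
- SAP 8.2.5 lists population a first, while 8.1.4 puts newly prescribed women first. The two sections need reconciling.
- Restriction to new users does not adjust for calendar time or equalise look-back.
- The two candidate covariates are not calendar time, and both face the p ≤ 0.20 screen.

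A reader might infer that 78 to 82% of the bisphosphonate cohort were continuing users, from 68,000 × 0.94 to 0.99 over 82,041. The documents do not support that. The 68,000 is a cross-sectional count carried over from the protocol, taken before the entry criteria are applied.

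**Conclusion.** The point holds for population a. The index rule lets continuing comparator users enter early, look-back has no common window, and nothing in the sampling, stratification or models uses calendar index date, or country in the pooled model. The arms may therefore differ in period and in completeness of history, and the planned tables would not reveal it.

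The size is not known. In Spain the illustrative gap in mean index date is 0 to 18 months with uniform uptake and 7 to 25 months with rising uptake, for a continuing-user share of 0 to 90%. These ranges rest on assumed distributions.

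A reader might infer that comparator history is less complete and that the bazedoxifene ratio is therefore biased downward. That is plausible at most within Spain. In the pooled data Italian comparators can have longer records than Spanish bazedoxifene women, so the look-back gap may shrink or reverse. The direction should be treated as uncertain.

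The change is worth making because it is standard when a newly launched drug is compared with established ones and uses data already recorded.

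**What to change.** - **SAP 8.1.4:** stratify the Cox models by calendar year of index (half-year only if events allow), and by country in the pooled model. Force these in, outside the p ≤ 0.20 screen. If the logistic fallback is used, enter both as fixed terms.
- **SAP 5.4:** add country and index year to the bisphosphonate sampling strata, set to the bazedoxifene distribution. Where a stratum holds fewer than six comparators per bazedoxifene woman, take all of them.
- **SAP 8.2.1:** report index date and length of prior record by cohort and country.
- **Sensitivity analysis:** for VTE, read history from the same fixed look-back window in every woman, limited to women whose records cover it.
- **SAP 8.1.4 and 8.2.5:** state which population the Cox model uses first.

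The cost is SAP wording and variables already in the data. Some precision is lost with only about 16 bazedoxifene VTEs expected, which is why year is preferred to half-year. Women with short records drop out of the fixed-window analysis. Raloxifene has no sampling step, so its crude comparison stays unbalanced on index date and relies on the stratified model.

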7 HANDLING OF MISSING VALUES

For each variable, the number and proportion of patients missing data for each treatment group will be specified. The primary analyses will be done using only the information available in the unmodified dataset. Smoking status, alcohol consumption, height and/or weight (BMI) values are known to be missing for approximately 40-60% patients in the Cegedim LPD based on previous studies. (Age of patients will always be known as it is a selection criterion). Dates are automatically recorded in the Cegedim LPD and doctors can select diseases codes from the pre-defined lists. In all analyses, if a condition (disease or treatment) other than the diagnosis of osteoporosis is not recorded, it will be assumed to be non-existent.

To estimate the effect of missing data, two additional analyses for the primary study endpoint will be conducted. First, the analyses will be repeated utilizing a dataset in which cases with missing values of main study covariates of BMI, smoking status and alcohol status are excluded. The disadvantage to this approach is the reduction in the sample size. Another disadvantage to this approach is that the subjects with missing values may be different than the subjects without missing values (e.g., missing values that are not missing at random), resulting in a non-representative sample after removing the cases with missing values. Second, multiple imputations for the missing values of BMI, smoking status, alcohol status will be used in the second set of analyses and compared to complete case analyses to understand the potential impact of missing data on results [2].

Outlier

Extreme values for weight and height will be searched for. If a value seems implausible, as regard to gender or ratio weight/height, it will be put as missing.

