Venous Thromboembolic Events (VTE) are defined as deep vein thrombosis, pulmonary embolism, retinal vein thrombosis, and venous sinus thrombosis. This objective is to compare this incidence in real life settings with validated diagnosis codes, ICD9 in Italy and International Classification of Primary Care (ICPC) codes in Spain.

The availability of medical history of all relevant medical diagnosis for patients will be checked in both the Spanish and the Italian database and presented if available. The variables of medical history (diabetes, hypertension, VTE and Malignancies) will be presented in classes (Yes/No) before index date. (All the detailed diagnosis codes of each endpoint have been validated by Pfizer and are available in a separate reference document). For all medical history and smoking status, if the relevant information is not found in the database, it will be assumed to be negative.

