8.2 STATISTICAL ANALYSES

8.2.1 PATIENT CHARACTERISTICS

Descriptive statistics on available patient characteristics (e.g. age, BMI, smoking, history of relevant medical diagnoses) will be reported for all exposure groups at index date. A summary table will present and compare all the patients' demographic data at index date (BZA/raloxifene/bisphosphonates).

- Age (years): derived by difference between the year of time of interest and year of birth.
- Weight (kg): recorded at the given date, or if not available, at the most recent date before or it
- Height (cm): the value at the given date or, if not available, at the most recent date before or after it.

- Body Mass Index (BMI) (kg/m^2), calculated from weight and height as defined previously. BMI will be described in quantitative measure and in categorical data, as usual
- Alcohol use
- Smoking status
- Time since diagnosis of osteoporosis: derived by the difference between the index date and the diagnosis date.
- Previous treatment for osteoporosis (before index date) (yes versus no) or Number of different treatments for osteoporosis in the entire patient history available
- Previous history of VTE (Venous Thromboembolic Events) (before index date)
- Previous history of major lower extremity (hip, knee) arthroplasty, arthroscopic surgery (information on arthroscopic surgery not available in Italian database)
- General surgery, major orthopedic surgery (<1month prior to incidence of VTE) (information on general surgery not available in Italian database)
- Multiple trauma, (<1month prior to incidence of VTE)
- Hip, pelvis, or leg fracture (<1month prior to incidence of VTE)
- Stroke (<1month prior to incidence of VTE)
- Acute spinal cord injury (paralysis) (<1month prior to incidence of VTE)
- Hormone replacement therapy (limited information available in both databases)

If the diagnoses for any of the conditions listed in this section (8.2.1) are not found in the database, they will be assumed to be absent.

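### The SAP treats every unrecorded condition except osteoporosis as absent, and no planned analysis tests this for endpoint history or for diabetes and hypertension

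*SAP*

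**What the plan says.** SAP section 7 sets the general rule for all analyses: "if a condition (disease or treatment) other than the diagnosis of osteoporosis is not recorded, it will be assumed to be non-existent". Section 8.1.1 repeats it: "For all medical history and smoking status, if the relevant information is not found in the database, it will be assumed to be negative". Section 8.2.1 says of its listed risk factors that, where diagnoses "are not found in the database, they will be assumed to be absent".

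Two parts of the analysis depend on this rule:

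- **Endpoint history (SAP 5.4).** "Women with a history of study end points recorded prior to the index prescription will not be included in the analysis" for that outcome. Exclusion therefore depends on a record being there.
- **Covariates (SAP 8.1.1 and 8.1.4).** "The variables of medical history (diabetes, hypertension, VTE and Malignancies) will be presented in classes (Yes/No) before index date". Diabetes, hypertension and malignancies are then candidate covariates in the Cox model.

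The one exempted condition is osteoporosis. SAP 2.1 plans a comparison of women with and without that diagnosis within 60 days of index, and gives the reason: "This has become necessary due to a significant number of patients (> 45%) missing a recorded diagnosis of osteoporosis".

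The missing-data analyses in SAP 7 and 8.2.5 cover BMI, smoking and alcohol only. On prescriptions, SAP 2.1 says: "The LPD databases of Italy and Spain contain all drug prescriptions". Both countries classify drugs by ATC.

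**The concern.** The study draws on general-practice records. SAP 2.1 requires only six months of prior history with at least one visit, and says that hospital information is not collected systematically. In such data a missing code is weak evidence that a condition is absent. The SAP's own osteoporosis figure is a reason to ask how complete the coding is, yet the assumption is left untested for every other condition.

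There are two possible consequences. Old disease that is first coded after index can be counted as new, which raises the rates and distorts the ratio. Diabetes and hypertension that are only partly recorded leave confounding in the adjusted hazard ratios. In a safety study, bias towards 1 can hide harm.

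**Working it through.** **The plan's figure.** The share above 45% comes without numerator, denominator or look-back, so it cannot be reproduced. The sample size used below does reproduce: 1,823 × 6 = 10,938.

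**Which endpoints have a safeguard.** Protocol 2.2 and 6.3 require record review to confirm the diagnosis.

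- Reviewed: VTE, ischemic stroke, thrombotic and ischemic cardiac disorders, five cancers (breast, ovarian, renal, thyroid, endometrial) and ocular events of vascular origin.
- Not on the review list: atrial fibrillation, biliary events, hypertriglyceridemia, fractures, renal failure, depression, goitre (thyroid disorders in the SAP), gastrointestinal and lung cancers, and other ocular events.
- Not touched by review: the covariates.

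**Illustration 1: VTE.** The documents give the rate I = 0.00174 per person-year (protocol 7.1). Everything else is assumed: q = share with an uncoded old VTE, c = yearly chance that it is coded, true ratio R = 2, no old case removed by review.

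Seen ratio = (I × R + q₁c) / (I + q₀c), with q₁ for bazedoxifene and q₀ for bisphosphonate.

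- q = 1% in both groups, c = 5%: old cases add 0.01 × 0.05 = 0.0005. Their share of comparator events is 0.0005 / 0.00224 = 22%. Seen ratio = 0.00398 / 0.00224 = 1.78.
- q = 0.5%, c = 2%: 0.00358 / 0.00184 = 1.95.
- q = 2%, c = 10%: 0.00548 / 0.00374 = 1.47.
- Unequal, q₁ = 0.5%, q₀ = 1%, c = 5%: 0.00373 / 0.00224 = 1.67.
- Unequal, q₁ = 2%, q₀ = 0.5%, c = 5%: 0.00448 / 0.00199 = 2.25.

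The seen ratio lies between R and q₁/q₀. With equal q it moves towards 1; otherwise it can go either way.

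A count-based cross-check uses 1,823 and 10,938 women and 3.42 person-years each (15% yearly loss, compounded over five years). True cases are 1,823 × 3.42 × 0.00348 = 21.7 and 10,938 × 3.42 × 0.00174 = 65.1. If 1% have an uncoded old VTE and 10% of these are coded during follow-up, 1.8 and 10.9 false cases are added. The seen ratio is [(21.7 × 0.99 + 1.8) / 1,823] / [(65.1 × 0.99 + 10.9) / 10,938] = 1.85. Across 0.5–2% uncoded, 5–45% later coded, and 3.42 or 4.25 person-years, it runs from 1.39 to 1.97.

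**Illustration 2: an unreviewed endpoint such as depression.** All inputs are assumed: 10% have the condition before index, 45% of them uncoded, 10% a year coded later, true incidence 10 per 1,000 in the other 90%, true ratio 1.5.

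- Old: 0.10 × 0.45 × 0.10 = 0.0045. New: 0.01 × 0.90 = 0.0090. Old share = 0.0045 / 0.0135 = 33%.
- Seen ratio = (0.0135 + 0.0045) / 0.0135 = 1.33. With 20% uncoded: (0.0135 + 0.0020) / 0.0110 = 1.41.

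**Illustration 3: an under-recorded covariate.** All inputs are assumed: hypertension 45% in bazedoxifene and 60% in bisphosphonate, risk ratio 2, 55% of it coded, no false codes, person-time 1:6, true drug ratio 1.

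- Crude: (1 + 0.45) / (1 + 0.60) = 0.906.
- The coded stratum contributes 0.440 to both the Mantel-Haenszel numerator and denominator. The uncoded stratum contributes 0.955 × 4.02 / 4.7725 = 0.804 and 5.64 × 0.7525 / 4.7725 = 0.889.
- Adjusted: 1.244 / 1.329 = 0.936. On the log scale, 0.066 / 0.098, or about two thirds, of the confounding remains.
- A milder case, 10% versus 20% with risk ratio 2, gives a ratio in the coded-absent stratum of 0.987 at 90% sensitivity, 0.970 at 75% and 0.951 at 55%.

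**The case against.** A reader might infer that about 45% of other conditions are uncoded too. The documents do not support that:

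- The figure is about osteoporosis only and stands beside a 60-day window test. A woman coded years earlier and still treated could be among those without a code. Endpoint history is any record before index, with data since 2004 in Italy and 2006 in Spain.
- A missing osteoporosis code may be correct, because bisphosphonates and raloxifene are also used for prevention (protocol 1.1 and 10).
- While the third inclusion criterion stands, women without the code in the window are not in the analysis. They enter only if the 20% comparison leads to the criterion being dropped.

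A reader might also infer that women with old uncoded disease will certainly become incident cases. They do so only if a code is entered later and, for reviewed endpoints, if the case passes record review. That weakens the concern for VTE. It does not remove it: the stated purpose of the review is to confirm the diagnosis, not the date of onset, and the SAP does not repeat the review.

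It is also fair to say that all the sizes above rest on assumed inputs. Prescribers may steer women with earlier VTE away from bazedoxifene, since VTE is on its label; uncoded history would then be unequal and the bias need not be towards 1. Finally, drug proxies have faults. Antidepressants are given for pain, and anticoagulants after orthopaedic surgery, which is itself a VTE risk factor listed in SAP 8.1.4. This argues against using such proxies to exclude women from the main analysis. It does not argue against a sensitivity analysis.

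**Conclusion.** The concern holds in a limited form. The rule is explicit, it decides who is at risk and how two covariates are coded, and no planned analysis tests it. It matters most for unreviewed endpoints such as depression and hypertriglyceridemia, and for diabetes and hypertension. It matters less for VTE and the other reviewed endpoints.

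The documents give no uncoded prevalence and no later-coding rate, so the size of the bias cannot be derived from them. The illustrations show only that modest under-recording could matter. With equal uncoded prevalence across drugs the ratio moves towards 1; with unequal prevalence the direction is open. This is a cheap improvement to the plan, not evidence that its results will be wrong.

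**What to change.** 1. In SAP 7 and 8.1.1, define diabetes and hypertension as present before index if coded or if there are pre-index prescriptions from a listed ATC group (glucose-lowering drugs, antihypertensives). Use this definition in the Cox models.
2. In SAP 5.4 and 8.1.3, add a sensitivity analysis that also excludes women whose pre-index prescriptions mark the endpoint: antidepressants for depression, fibrates for hypertriglyceridemia. Add one for VTE without women on pre-index anticoagulants, and state its limits, including that some of these women were treated for other reasons and may be at high risk of a new VTE.
3. Carry the record review of protocol 6.3 into the SAP, with a check that onset is after index.

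The SAP should also state the numerator, denominator and look-back of the share above 45%.

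The cost is an ATC list, a few lines of SAP text and code, and one extra item in the record review. Prescriptions already define prior treatment in the new-user subgroup (SAP 5.4), so the method is not new to the plan. The downside is that some drugs are not specific: some disease-free women will be classed as having diabetes or hypertension, or will leave the risk set of a sensitivity analysis. Endpoints without a usable drug marker, such as biliary events or fractures, remain untested.
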